Study Protocol and Statistical Analysis Plan

Title: The Influence of Topical Capsaicin on Thermoregulatory and Perceptual Outcomes During Exercise Within the Heat

NCT05298202

Unique Protocol ID: 0192-22-FB

Date: 25 May 2022

Abstract

The purpose of this study is to examine the human thermoregulatory impact of applying a commercially available capsaicin cream to the skin prior to moderate intensity walking under heated conditions. Eligible participants will be aged 19-45 years, have no previously known adverse reactions to capsaicin (active ingredient) based upon a self-report, no adverse reactions to capsaicin as determined through application to a small forearm area, and cleared for physical activity via the 2022 Physical Activity Readiness Questionnaire (PARQ). There will be a total of 3 experimental visits to the laboratory. Visit 1 will test for adverse capsaicin reaction by applying a small amount of cream to the forearm ($\sim 2 \times 2$ in). Anthropometric and body composition data will also be collected at this time. Visits 2 and 3 will consist of 30 min of treadmill walking at a moderate pace (3.5 mph, 5% grade) under hot conditions (38°C, 60%RH). Visits 2 and 3 will be randomized and counterbalanced for capsaicin or a hypoallergenic cream (control) application. Creams will be applied to areas commonly exposed during outdoor activity in warm conditions (shoulder to wrist, mid-thigh to ankle). Accordingly, participants will wear shorts and a tank top shirt during exercise. Core temperature, skin temperature, galvanic skin response, laser doppler blood flow, and heart rate will be continuously recorded throughout the exercise bout via an integrated analog to digital converter. Sweat will be collected during exercise using commercially available absorbent patches. Thermal sensation will be assessed throughout exercise via the ASHRAE thermal sensation Likert scale (cold to hot). Lastly, nude body weight will be recorded pre and post exercise for sweat rate determination. The capsaicin and control trials will be separated by a 7-14 day washout period. There will be no follow up visits.

Purpose and Rationale

The purpose of this study is to examine the impact of applying a capsaicin-based cream to the skin on human thermoregulation and thermal perception during exercise in the heat. The capsaicin chemical compound is found in many hot sauces, making it strongly associated with feelings of heat and pain. Topical capsaicin receptors can invoke a tingling sensation that can be perceived as heat. The capsaicin receptor is a part of a family of membrane proteins called transient receptor potential (TRP) channels [1]. TRPs allow for the perception of environmental stimuli and act as sensory mediators. The capsaicin receptor in our body, also known as vanilloid receptor one, is a TRPV1 channel. Besides activation of the TRPV1 channel by capsaicin, it is also activated by ambient noxious heat [1,3]. Capsaicin activated TRPV1 receptors lead to vasodilation of the skin [1]. This vasodilation is vital to the cooling of the body, as it gets rid of excess heat, aiding in thermoregulation. This can be contradictory to the perceived heat since it aids in cooling. It was first discovered that TRPV1 plays a role in thermoregulation when it was found that capsaicin has hypothermic action that can lower core temperature significantly in multiple species, including humans [2]. This evidence supported that TRPV1 has profound effects on maintaining homeostasis of internal body temperature.

If topical capsaicin provokes vasodilation, then the question remains as to why it is not more commonly used by humans in hot environments. This could be because of the previously referenced negative feelings of capsaicin. Currently, topical capsaicin creams are marketed as an analgesic, commonly aimed at those experiencing arthritic pains; yet this is not their full physiological potential. There is a physiological conflict between the perceived hot sensation of capsaicin compared to the observed physiological effects. It is currently unknown if over-the-counter capsaicin creams can aid in performance during exercise in the heat, or if the perceived burning sensation would hinder

performance. This requires further investigation into the effects that topical capsaicin may have on exercise performance in the heat.

Participants

12-15 subjects, aged 19 to 45, will be needed to complete the study. Keeping the age range of 19-45 ensures that the participants will be of consenting age and cleared for physical activity participation.

Research Plan

Three experimental visits to the laboratory will be conducted. All visits will take place at the University of Nebraska at Omaha, Exercise Physiology Laboratory. Visit 1 will consist of the physical activity readiness questionnaire (PARQ), adverse reaction to Rugby Capsaicin Cream (0.025%), and body composition (hydrostatic weigh, bioelectrical impedance). Visits 2 and 3 will be separated by 7-14 days, randomized, and counterbalanced for experimental (capsaicin) and control (hypoallergenic cream) trials. Both the experimental and control visits will follow the same protocol.

Participants will arrive following an overnight fast state while also refraining from strenuous activity, alcohol consumption, tobacco use, and recreational drugs for the previous 24 hour period. During these visit researchers will apply Rugby capsaicin cream using a gloved hand from shoulder to wrist and mid-thigh to ankle (areas outside of the clothing). A hypoallergenic cream (Remedy Essentials Unscented Moisturizing Body Lotion, Medline Industries inc.) will be applied during the control visit.

Exercise will consist of 30 min of moderate intensity treadmill walking (3.5 mph at 5% grade) within a heated temperature/humidity-controlled chamber (38°C, 60% relative humidity).

Participants will be weighed before, and after completion of the exercise calculate sweat rate. Prior to the exercise session, participants will sit for 5 min in an ambient room temperature environment as a baseline. During baseline and during the exercise core temperature, skin temperature, laser doppler blood flow, galvanic skin response, and heart rate will be collected continuously. Sweat patches will be adhered to the forehead during exercise at minute 10 for collection of sweat composition over the next 10-20 minutes.

Thermal perception using the ASHRAE scale (cold to hot) will be assessed pre and during exercise.

EXPERIMENTAL VISIT 1

Visit 1 will take approximately 1 hour. Participants will then complete the physical activity readiness questionnaire (PARQ) to be cleared for physical activity. Participants will have a small amount of the capsaicin cream and control cream applied to a small area of the forearm (~2 x 2 in) to test for any adverse reaction over a period of 15 minutes. Those without a reaction will have height, weight, and body fat composition measured. Then, resting blood pressure and heart rate will be taken. Those without a reaction, and a resting blood pressure lower than 140/90, will have height, weight, and body fat composition measured. Height and weight will be measured using a medical scale and stadiometer, respectively. Body fat will be assessed with hydrostatic weighing using an electronic load cell-based system (Exertech, Dresbach, MN) correcting for residual lung volume or via a bio- electrical impedance analyzer (InBodyUSA, Cerritos, CA).

EXPERIMENTAL VISITS 2 AND 3

Visits 2 and 3 will take approximately 2 hours each. Upon arrival at the lab, a nude body weight will be collected with the subject in a private room. While still in the room, subjects will self-insert a rectal

thermistor 12-15 cm beyond the anal sphincter and don a chest strap heart rate monitor. After dressing in their exercise clothing, subjects will exit the private room so that chest, forearm, and calf thermistors can be adhered to the skin with tape.

Laser doppler flow (forearm and/or/finger) will be adhered with tape and galvanic skin response (fingers) will be adhered using Velcro straps to the skin. Measuring instruments will be recorded using an integrated digital to analog converter (ADInstruments, Colorado Springs, CO).

Following instrumentation, subjects will sit for 5 minutes as a baseline for all recordings in a temperate environment. Immediately after, a researcher with gloved hands will topically apply capsaicin or the control hypoallergenic cream from the shoulder to wrist and mid-thigh to ankle. Subjects will then enter the heat chamber (38°C, 60% relative humidity) and immediately begin a 30-minute walk on a treadmill (3.5 mph, 5% grade). Subjects will be intermittently asked to hold their arm steady for laser doppler flow collection (10, 20, 30 minutes). Subjects will also briefly pause at minute 10 in order to adhere an absorbent patch to their forehead for sweat collection over the following 10-20 minutes. Thermal perception using the ASHRAE scale (cold to hot) will be assessed pre and during exercise. After 30 minutes of walking, subjects will exit the chamber for removal of all skin and finger sensors. Subjects will then re-enter the private room, remove their own rectal thermistor with gloved hands, and then a final nude body weight will be recorded after toweling off.

The rectal thermistor will measure core temperature. The heart rate monitor will measure the beats of the heart. Skin thermistors will measure the temperature of the skin surfaces. Laser doppler flow measure the relative units of blood flow velocity. Galvanic skin response measures skin conductivity changes as individuals begin to sweat. Sweat is collected for assessment of sweat composition. Thermal perception is assessed for individual perception surrounding the temperature of the ambient environment. Nude body weight is measured to calculate sweat rate.

Statistical Analysis

Recruitment

Previous exercise research suggests that the difference in response of matched pairs is normally distributed with a standard deviation of 0.86. If the true difference of the mean response of matched pairs is 0.75, we will need to complete 12 experimental trials for each condition to be able to reject the null hypothesis that this response difference is zero with a power of 0.8. The Type I error probability associated with this test of the null hypothesis is 0.05.

Interventions

A repeated measures two-way ANOVA (Time x condition) will be used for the dependent variables. If the F-ratio values are found to be significant, a Fisher's Least Significant Difference post hoc analysis will be conducted. A type I error probability of < 5% will be considered significant ($p < 0.05$). All data will be analyzed using a combination of Microsoft Excel and the Statistical Package for the Social Sciences (SPSS).

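### The visit order is randomised and counterbalanced, but the planned ANOVA has no period or order term, so any shift between the two heat walks stays in the error for the condition effect

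*Combined protocol and SAP*

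**What the plan says.** The Abstract states that "Visits 2 and 3 will be randomized and counterbalanced for capsaicin or a hypoallergenic cream (control) application", and the Research Plan repeats this with the interval: "Visits 2 and 3 will be separated by 7-14 days, randomized, and counterbalanced for experimental (capsaicin) and control (hypoallergenic cream) trials". Each person therefore does the same heat walk twice, once per cream, in one of two orders.

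Under Statistical Analysis (Interventions) the model is given in one sentence: "A repeated measures two-way ANOVA (Time x condition) will be used for the dependent variables". Fisher's LSD follows a significant F. No section mentions a period, visit, order or sequence term.

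Under Experimental Visits 2 and 3, some outcomes yield one value per visit: "Nude body weight is measured to calculate sweat rate", and one forehead patch gives the sweat composition. Recorded signals also have a resting value before the cream goes on: "Following instrumentation, subjects will sit for 5 minutes as a baseline for all recordings in a temperate environment".

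The sample size (Statistical Analysis, Recruitment) is a paired calculation assuming that "the difference in response of matched pairs is normally distributed with a standard deviation of 0.86". Under Participants, "12-15 subjects, aged 19 to 45, will be needed to complete the study".

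**The concern.** Counterbalancing protects the estimate against a visit effect, but the analysis has to use the order for the standard error to benefit. Suppose responses at visit 3 differ systematically from those at visit 2, for example because the second walk is more familiar. The capsaicin-minus-control difference then contains plus the shift for people who get capsaicin second, and minus the shift for those who get it first. An ANOVA on time and condition cannot tell this pattern from random variation between people, so it goes into the subject-by-condition error.

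Three results follow:

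- **Equal orders:** the estimate is unbiased, but its standard error is too large, intervals are too wide and the test rejects too rarely.
- **Unequal orders:** the estimate also moves. This is certain with 13 or 15 completers and possible at any total after dropout.
- **Time-by-condition interaction:** a shift that is constant within a visit cancels, because each visit has its own baseline. Only a shift that changes over the 30 minutes reaches this test.

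At stake is a missed or imprecise condition effect in a trial of 12 to 15 people. With equal orders there is no extra false-positive risk.

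**Working it through.** **Inputs.** From Statistical Analysis (Recruitment): mean paired difference δ = 0.75, SD of paired differences σ = 0.86, type I error 0.05 (taken as two-sided, since the null is a zero difference), power 0.8, 12 trials per condition. From Participants: 12 to 15 completers. Assumed, because the documents do not give it: a visit-3-minus-visit-2 shift π between 0 and 1 SD (0 to 0.86 units).

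**The plan's own figure.** The normal approximation gives n = (0.86 × (1.960 + 0.842) / 0.75)² = 10.3, so 11. Exact paired-t power is 78.5% at n = 12 and 82.3% at n = 13. The stated 12 is reproduced to within rounding of the power.

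**Model.** For person i, dᵢ = δ + sᵢπ + eᵢ, with sᵢ = +1 if capsaicin is at visit 3, −1 if at visit 2, and SD(e) = 0.86. Let n₁ and n₂ be the completers per order and n their sum.

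- Planned comparison (condition main effect, or a plain paired test of a single-value outcome): the mean of the dᵢ with n − 1 df. Its bias is π(n₁ − n₂)/n.
- At 6/6 the expected error variance is multiplied by 1 + (12/11)(π/σ)²: 1.07 at 0.25 SD, 1.27 at 0.5 SD, 2.09 at 1 SD.
- Period-adjusted comparison: the average of the two order-specific means of dᵢ, with n − 2 df and SE = 0.5 × 0.86 × √(1/n₁ + 1/n₂). At 6/6 this is 0.43 × √(1/3) = 0.248, whatever π is.

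**Results at 6/6.** Unadjusted figures come from integration over a noncentral chi-square error term, adjusted ones from the noncentral t.

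| Shift (SD) | Power, no period term | Power, with term | Type I error, no term |
|---|---|---|---|
| 0 | 78.5% | 77.7% | 5.0% |
| 0.1 | 78.2% | 77.7% | 4.9% |
| 0.25 | 76.4% | 77.7% | 4.4% |
| 0.5 | 70.1% | 77.7% | 3.0% |
| 0.75 | 59.8% | 77.7% | 1.6% |
| 1 | 46.3% | 77.7% | 0.6% |

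The two power curves cross at about 0.16 SD. Simulation (200,000 runs per case) shows the mechanism: from 0 to 1 SD the true SD of the estimate stays at 0.248, while the mean estimated SE rises from 0.243 to 0.353.

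**Unequal orders, shift 0.5 SD = 0.43 units.**

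- 8/7: bias 0.43/15 = 0.029, or 3.8% of 0.75.
- 7/6: bias 0.43/13 = 0.033, or 4.4%.
- 7/5: bias 0.43 × 2/12 = 0.072, or 9.6%. Unadjusted power is 78.6% or 61.0%, depending on the direction of the shift, against 76.6% with the term.

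**Time-by-condition test at 6/6.** This is an illustration on assumed inputs: four time points, SD 0.86 per point, correlation 0.5, sphericity, and an effect growing to 0.75 (60,000 simulations per case). A constant shift of 0 to 1 SD leaves power at 71% and type I error at 5%. A shift growing from 0 to 0.5 SD over the walk gives 66%, against 70% with an order factor. One growing to 1 SD gives 51% against 70%.

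**The case against.** The strongest reply is that the harm depends on a shift nobody has shown to exist. The visits share one protocol, with fasting, 24-hour restrictions and a controlled chamber, and they are 7 to 14 days apart. Below 0.16 SD the planned test is marginally better, and at 0.25 SD the term gains only 77.7 − 76.4 = 1.3 points. The large losses need shifts of 0.75 SD or more. This stands, and it is why the impact is uncertain. On the other side, Visit 1 includes no practice walk or heat exposure, so a shift cannot be ruled out.

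Second, 0.86 may already contain a shift if it came from unadjusted crossovers. Holding the total SD at 0.86, planned power at 6/6 is 79% for a shift of 0.25 units and 83% for 0.50 units, so there is no shortfall against plan. This also stands. In that case the term would raise power, to 81.5% and 92.8%.

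Third, more completers soften the loss. At 8/7 and 0.5 SD, unadjusted power is 79% or 85% by direction, against 87.6% with the term. Type I error stays below 5% under mild imbalance (3.6% at 7/5, 3.1% at 7/6 and 8/7). Both points are correct.

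Fourth, baseline precedes the cream, so if it is a level of time, a capsaicin effect shows chiefly in the interaction, which a constant shift leaves alone. That is right and limits the concern to the condition main effect and single-value outcomes, unless the shift grows during the walk.

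Fifth, a time-by-condition ANOVA cannot be fitted to one value per visit, and the plan names no other test for sweat outcomes. The figures above assume a plain paired test there. That gap is a further reason to specify the analysis.

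**Conclusion.** The concern holds. The design controls visit order, the analysis ignores it, and nothing elsewhere in the documents fills the gap. The algebra is certain; the practical size is not, because it depends on an unknown shift.

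At 12 completers split evenly, omitting the term changes power by +0.8 points with no shift, −1.3 at 0.25 SD, −7.6 at 0.5 SD and −31 at 1 SD, relative to including it. These figures take 0.86 as the SD without any shift. Bias is zero with equal orders and, at a 0.5 SD shift, between 0.029 and 0.072 for splits of 8/7 to 7/5. With equal orders the test errs only on the conservative side.

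This is therefore a matter of precision and power that should be corrected because the correction is nearly free. It does not threaten the trial's validity.

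**What to change.** State in the SAP that visit order enters the analysis.

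- **Repeated outcomes:** in the SPSS repeated-measures GLM, add order as a between-subject factor with its interactions, and average the condition and condition-by-time effects over the two orders with equal weight. Alternatively, fit a mixed model with condition, time, condition by time, period, period by time, and sequence.
- **Sweat rate and sweat composition:** use the period-adjusted paired comparison, which is half the between-order difference in visit-3-minus-visit-2 change, on n − 2 df.
- **Reporting:** give the number of completers in each order.

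Only the wording changes; each person's order is known from the allocation and no new data are needed. The condition contrast loses one degree of freedom. If there is no shift, power goes from 78.5% to 77.7% at 6/6, 78.5% to 76.6% at 7/5, 82.3% to 81.4% at 7/6, and 88.1% to 87.6% at 8/7. With order as a factor, the interaction error loses one degree of freedom for each time point after the first (three with four time points), which costs under one power point in the illustration.

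### The forearm tolerance test is read over 15 minutes at Visit 1, and no later look or question about a delayed reaction is scheduled before cream goes on the arms and legs

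*Combined protocol and SAP*

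**What the plan says.** The Abstract makes tolerance an eligibility condition in two ways: a self-report of no known reaction, and "no adverse reactions to capsaicin as determined through application to a small forearm area". The second carries no time limit.

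The section on Experimental Visit 1 gives the procedure. Capsaicin and control cream are applied to roughly 2 x 2 in of forearm "to test for any adverse reaction over a period of 15 minutes". Blood pressure and heart rate follow, and the no-reaction condition is then stated again: "Those without a reaction, and a resting blood pressure lower than 140/90, will have height, weight, and body fat composition measured". No time or second inspection is attached to that repeat. The visit lasts about an hour.

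The section on Experimental Visits 2 and 3 begins with nude weight, rectal thermistor and heart rate strap. The participant then comes out "so that chest, forearm, and calf thermistors can be adhered to the skin with tape". After a 5-minute baseline: "Immediately after, a researcher with gloved hands will topically apply capsaicin or the control hypoallergenic cream", over the arms and from mid-thigh to ankle. The walk lasts 30 minutes at 38°C and 60% relative humidity. Sensors are removed after it, and "a final nude body weight will be recorded after toweling off".

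**The concern.** The forearm test exists to find people who should not have capsaicin spread over all four limbs. Its scheduled reading ends at 15 minutes, and nothing later in the schedule returns to the question. The eligibility criterion is open-ended, but the procedure that serves it looks only once, early.

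Someone whose skin reacts an hour or a day later would meet the plan's definition of ineligible. They would still go on to full-limb application unless they mentioned it or a member of staff happened to see it. What is at stake is the comfort and safety of individual participants. Nothing in the estimate, the error rate or the power depends on it.

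**Working it through.** The plan computes no figure on this point, so the check compares the scheduled steps.

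1. **Test reading.** 15 minutes, on about 2 x 2 in (Experimental Visit 1).
2. **Later contact.** Application, then a 30-minute walk, then chamber exit, sensor removal and thermistor removal, then drying with a towel, which is the first listed step that would take cream off (Experimental Visits 2 and 3). Contact = 30 min + untimed application + untimed removal steps, so more than 30 min. If application and removal take 5 to 10 minutes each (an assumption), contact is 30 + 5 + 5 = 40 to 30 + 10 + 10 = 50 minutes.
3. **Are the two comparable?** Not directly. The first is a reading window and the second is contact time. The like-for-like figure would be contact time of the test cream, which is not stated. If the cream is wiped off at the reading, test contact is 15 minutes. If it is left on, it could run through the rest of the visit of about 60 minutes, or longer. The difference 30 - 15 = 15 minutes therefore does not measure under-testing.
4. **Is there a later check in Visit 1?** At most 60 - 15 = 45 minutes of the visit lie outside the reading, with staff present. The repeated no-reaction condition falls in that time, but no inspection goes with it.
5. **Is there a check between Visit 1 and full-limb cream?** The listed order at Visit 2 is nude weight, sensors, baseline, cream. It has no skin inspection and no question. The interval from Visit 1 to Visit 2 is not given; the Research Plan fixes only the next one: "Visits 2 and 3 will be separated by 7-14 days, randomized, and counterbalanced for experimental (capsaicin) and control (hypoallergenic cream) trials". A reaction could have come and gone before Visit 2, so a look alone would not be enough.
6. **Who would a Visit 2 check cover?** The Participants section says "12-15 subjects, aged 19 to 45, will be needed to complete the study". With an even counterbalance, 12/2 = 6 to 15/2 = 7 or 8 people receive capsaicin at Visit 2, and the rest at Visit 3. A check on arrival at Visit 2 comes before full-limb capsaicin in both orders, so it covers everyone.

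**The case against.** The case on the other side is substantial and narrows the point.

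- **No evidence of late reactions.** The documents do not say that reactions to a 0.025% cream begin after 15 minutes, or that a skin test must be read for as long as the later exposure lasts. This stands: no rate or benefit can be claimed.
- **Unlike times.** A reader might infer that the test exposes the skin for less than half the time of the trial application. The documents do not support this, because they do not say when the test cream comes off. This stands too.
- **Already partly covered.** A late reaction that is noticed or reported would exclude under the Abstract criterion. The no-reaction condition is stated twice, and staff attach a forearm sensor before cream at Visit 2. This is true but incomplete. The repeat has no reading attached, and the documents do not say that the sensor goes on the tested arm.
- **Removed text.** Consent pages are not available and may ask participants to report late reactions. The point is therefore confined to the scheduled procedures.
- **A loose question could do harm.** Purpose and Rationale describes tingling, perceived heat and skin vasodilation as capsaicin's ordinary effects. Excluding anyone who reports any delayed reaction could remove strong responders from a study that measures thermal sensation. This stands and shapes the fix.

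**Conclusion.** The point holds as a low-severity safety suggestion. The only scheduled physical tolerance check before full-limb cream is a single 15-minute reading of a small forearm area. Nothing scheduled afterwards would detect a reaction that appeared later.

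Its size is unknown. All 12-15 participants are due one full-limb capsaicin application, but the number who might react late cannot be derived from the documents. The cream is a commercial 0.025% product, and people with known reactions are already excluded, which limits the concern further.

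A reader might go on to infer that the screening is unsafe, or that a person with a late reaction would be knowingly enrolled. Neither follows: no reaction rate is given, and the criterion as written would exclude a late reaction once known. The verdict rests on the scheduled steps being complete as listed, and on no reporting instruction standing in the removed consent pages.

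**What to change.** On arrival at Visit 2, before instrumentation and any cream, inspect the test site and ask whether an adverse reaction appeared after Visit 1. Define in advance what excludes: for example blistering, hives, swelling, or burning that persists or cannot be tolerated. State that transient warmth, tingling or redness does not.

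Participants come to Visit 2 fasted, and an exclusion after the order is assigned could disturb the counterbalance. Where practical, put the question by message before the fast and before the order is assigned, and keep the look for arrival.

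A further reading later in Visit 1, before any hydrostatic weighing, is optional. At 30 minutes it would leave 60 - 30 = 30 minutes of the visit outside the test period, and blood pressure, heart rate, height, weight and bioimpedance could fill the wait. It would still be shorter than the later contact and would not reproduce the heat, the exercise or the treated area, so it should not replace the Visit 2 check.

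The cost is one or two sentences of protocol and a line to record the answer, with no added visit or equipment. The downsides are an occasional late exclusion, which must be replaced to reach the 12 completed pairs that the sample-size paragraph calls for, and a slight selection against people with strong skin reactions.

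### Laser Doppler is in relative units with a new probe placement for each condition, and the plan names neither a scale nor a use of the same-visit baseline as reference

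*Combined protocol and SAP*

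**What the plan says.** Experimental Visits 2 and 3 describes the unit: "Laser doppler flow measure the relative units of blood flow velocity". On attachment it says: "Laser doppler flow (forearm and/or/finger) will be adhered with tape". The sensors come off at the end of each session: "After 30 minutes of walking, subjects will exit the chamber for removal of all skin and finger sensors". Within a visit, therefore, one placement serves both rest and exercise. The resting reading precedes the cream: "Following instrumentation, subjects will sit for 5 minutes as a baseline for all recordings in a temperate environment". Doppler is then read with the arm held still at 10, 20 and 30 min.

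The two conditions fall on different days (Research Plan): "Visits 2 and 3 will be separated by 7-14 days, randomized, and counterbalanced for experimental (capsaicin) and control (hypoallergenic cream) trials".

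Statistical Analysis, Interventions, gives one method for every outcome: "A repeated measures two-way ANOVA (Time x condition) will be used for the dependent variables". It mentions no transformation, calibration, percent of baseline or change from baseline. It does not say whether baseline is a level of Time, or which ANOVA term answers the question.

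**The concern.** Relative units carry no common zero-to-full scale across patches of skin. If a new placement multiplies all readings of a visit by some factor, that factor differs between a participant's capsaicin and control visits, and pairing within the participant does not remove it. It adds to the error of the condition comparison. On the untransformed scale, the same percentage effect is also a large difference in a high-flux placement and a small one in a low-flux placement, so a few participants dominate the error term.

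The rationale rests on capsaicin widening skin vessels, and Doppler is the only direct measure of skin blood flow listed. A weak test here could miss the mechanism. A mean difference in arbitrary units could not be interpreted across participants even if it reached significance.

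**Working it through.** **The plan's own figure.** Statistical Analysis, Recruitment, assumes that "the difference in response of matched pairs is normally distributed with a standard deviation of 0.86", with a true difference of 0.75, power 0.80 and alpha 0.05. The normal approximation gives [0.86 × (1.960 + 0.842) / 0.75]² = 10.32, so 11 pairs. Iterating with the t distribution gives 12.37, and exact two-sided power at 12 pairs is 0.785. The stated 12 is reproduced within rounding. It names no outcome, so it promises nothing for Doppler.

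**Model.** Flux = person level × visit gain × time mean × condition effect × reading noise. The gain is constant within a visit. A CV of c becomes a log variance of ln(1 + c²).

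**Inputs from the documents.** 12 pairs; readings at baseline, 10, 20 and 30 min; cream applied after baseline, so any effect appears only in the exercise readings.

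**Inputs assumed.**
- Effect +25%: ln 1.25 = 0.2231.
- Rest 15 units, exercise 60/75/80 units; between-person CV 35–60%.
- Exercise noise CV 15%: variance 0.0223.
- Baseline noise CV 15–30%: variance 0.0223–0.0862.
- Gain CV 20%: variance 0.0392. Gain CV 30%: 0.0862.

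**Step 1: log alone in the 2×4 ANOVA, condition main effect.** Averaging in the pre-cream baseline dilutes the effect to 3/4 × 0.2231 = 0.1674, and the gain remains. At gain CV 20% and baseline noise 15%, the SD of the paired difference is √{2 × [0.0392 + (3 × 0.0223 + 0.0223)/16]} = 0.299. The noncentrality is 0.1674 × √12 / 0.299 = 1.94, and power is about 42%.

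**Step 2: log exercise readings only, no baseline.** SD = √{2 × [0.0392 + 0.0223/3]} = 0.305; noncentrality 0.2231 × √12 / 0.305 = 2.53; power about 64%. The dilution is gone and the gain is still there.

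**Step 3: log exercise readings with the log baseline as covariate.** The gain variance g is replaced by g·b/(g + b), where b is the baseline noise variance.
- Baseline noise 15%: 0.0392 × 0.0223 / 0.0615 = 0.0142; SD = √{2 × (0.0074 + 0.0142)} = 0.208; noncentrality 3.72; power about 92% on 10 df.
- Baseline noise 30%: 0.0392 × 0.0862 / 0.1254 = 0.0269; SD = √{2 × (0.0074 + 0.0269)} = 0.262; noncentrality 2.95; power about 76%.

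Simulation gives 90% and 72%, slightly lower because the covariate slope must be estimated.

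**Step 4: simulated power across the assumed ranges.**

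| Gain CV | Raw 2×4 ANOVA | Log 2×4, condition effect | Log 2×4, interaction (baseline noise 15% / 30%) | Log flux with log baseline covariate |
|---|---|---|---|---|
| 10% | 87–92% (condition effect) | 76–85% | 71–72% / 42–43% | 95–97% |
| 20% | 47–60% (both terms) | 39–43% | 70–71% / 43% | 72–90% |
| 30% | 25–44% (both terms) | 23–24% | 71% / 42–43% | 55–84% |

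The covariate analysis beat both raw ANOVA terms in all 16 settings tried (gain CV 10–40%), with false positives near 5%.

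**Which change does the work.** With a single exercise reading of 80 units, raw against log power at gain CV 20% is 40–47% against 52% without baseline, and 41–59% against 56–69% with the baseline covariate. At 30% it is 24–29% against 32–33%, and 29–48% against 45–66%. Both changes contribute, and neither alone does as well as the two together.

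**False positives.** In a second model (gain log-SD 0–0.5, time means 1/3/4/4.5), the raw condition effect rejected in 4.2–4.8% of null trials at 12 pairs. The raw interaction without a sphericity correction ranged from 5% to 9%.

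**The case against.** The strongest reply is that the plan never says raw scale, that every variance above is assumed, and that the direction of a log-against-raw comparison depends on choices the plan leaves open. All of that stands. The untransformed scale is what the stated ANOVA yields if nothing is added; it is an inference from silence, not a declared choice.

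A reader might go further and infer that taking logs by itself recovers the lost power. The documents do not support that. Logging turns the gain into an additive visit offset that stays in the condition main effect. In the 2×4 layout that the readings suggest, log power for that effect was below raw in every cell with gain CV 10–30%. The log interaction does cancel the offset, but loses to raw when baseline is noisy and gain variation is small (42–43% against 67–76% at gain CV 10% and baseline noise 30%).

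A reader might also infer that the condition comparison is biased. It is not: the gain is unrelated to condition under randomised order, so it costs precision.

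Finally, Doppler is one of several outcomes and no primary outcome is named. That limits the weight of the point but does not remove it.

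**Conclusion.** The point holds as a gap in specification with a likely cost in precision and interpretation. It is not a threat to the validity of the condition contrast. The interpretation problem needs no assumed variance: a mean difference in relative units, pooled over separate placements, has no common meaning, whereas a ratio does.

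The gain in power is large if placement gain varies by 20–30% and small at 10%. The documents do not say which applies. The figures rest on a multiplicative gain that is constant within a visit. An additive offset would weaken the fix, and so would a probe that shifts during walking or while cream is applied to the arm after the baseline reading. The change is worth making before analysis because the data it needs are already being recorded.

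**What to change.** Add to Statistical Analysis, Interventions, for laser Doppler only:

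- Analyse log flux at 10, 20 and 30 min, with the same-visit pre-cream log baseline as a covariate and not as a level of Time.
- Name the capsaicin–control condition effect as the test of interest.
- Report the capsaicin/control ratio with its 95% CI.

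With two visits this is a regression of each participant's difference in mean log exercise flux on the difference in log baseline. The intercept, exponentiated, is the ratio. A covariate is safer than simply dividing by baseline, because division carries the full noise of the resting reading into the result. Percent of baseline performs much like log change from baseline (70% against 72% power in the second model, with ratio 1.3, gain log-SD 0.3 and residual log-SD 0.2). Naming one probe site, used at both visits, would also limit placement variation at its source.

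The cost is a few sentences and a one-line transformation. Results then read as percent change, not units, and one degree of freedom goes to the covariate (10 instead of 11 with 12 pairs). No new data are needed.
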